#### 6.2.1 Primary Endpoint(s)

The primary endpoint in Part A is the ABR of all bleeding episodes (sum of spontaneous bleeds and trauma bleeds exclude bleeding due to surgery) during prophylaxis treatment, and it will be summarized by age group ( $<12$  y,  $\geq 12$  y) separately.

The primary endpoint in Part B is the ABR of all bleeding episodes (sum of spontaneous bleeds and trauma bleeds exclude bleeding due to surgery) within 48 hours of a previous prophylaxis infusion.

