## **7.3 Efficacy Assessments**

The primary efficacy variable in Part A is the ABR of all bleeding episodes during prophylaxis. The ABR of all bleeding episodes within 48 hours of a previous prophylaxis infusion is the primary efficacy variable in Part B. The ABR of all bleeding episodes during prophylaxis in Part B and the ABR of all bleeding episodes within 48 hours of a previous prophylaxis infusion in Part A will be assessed as secondary efficacy parameters.

Additionally, the ABR for the following efficacy variables will be summarized for both Part A and Part B:

- Treated bleeding episodes
- Joint bleeding episodes
- Joint bleeding episodes within 48h of previous prophylaxis infusion
- Target joint bleeding episodes
- Spontaneous bleeding episodes
- Spontaneous bleeding episodes within 48h of previous prophylaxis infusion
- Spontaneous joint bleeding episodes
- Trauma bleeding episodes
- Trauma bleeding episodes within 48h of previous prophylaxis infusion

Other efficacy variables include:

- Minor surgery bleeding control
- Participants'/parents'/physician's (in case of surgery) assessment of the response to treatment of bleeding episodes (excellent, good, moderate, or poor)
- The number of infusions required to treat a bleeding episode
- Factor VIII usage (expressed as number of infusions and IU/kg per year, as well as IU/kg per event)
- Extent of exposure in terms of exposure days (EDs)
- Type, location, and severity of bleeding episodes
- Reason for each infusion
- Incremental recovery

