#### **9.4.2 Primary Endpoint(s)**

All efficacy analyses will be performed on the mITT population. In case of PP population (Part A only), more than 5% of participants in one arm (children or adolescents/adults) are excluded from the mITT population, and analyses for primary and secondary endpoints will be repeated in the PP population. As the non-adherence to the EPD documentation is considered independent from the treatment efficacy, the exclusion of participants without bleeding/infusion data from the EPD does not interfere with the intention-to-treat principle. These participants are excluded in order not to dilute the treatment effect.

The primary endpoint in Part A is the ABR of all bleeding episodes during prophylaxis treatment, and it will be summarized by age group (<12 y, ≥12 y) separately.

The primary endpoint in Part B is the ABR of all bleeding episodes within 48 hours of a previous prophylaxis infusion.

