### *Missing or incomplete concomitant medication start and end date or time:*

When computing concomitant medication start dates, if day is missing, it will be imputed as the 15th of the month. If month and day are missing, it will be imputed as 1 July. If necessary, adjust imputed dates so they are not before the birth date.

Other missing data will not be imputed.

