### **4.5 Data Rules**

All bleed and infusion data will be entered into the electronic patient diary (hospital infusions will be entered into an eCRF) and imported into SAS. If an infusion is given for a bleed and the bleed information is not provided, the infusion date will be used as the bleed date. Bleeds occurring before start of prophylaxis treatment with study medication will not be counted.

Bleeding rate will be annualized using the following formula:

Annualized bleeding rate [per year] =

365.25 [days per year] x (# of bleeding episodes in treatment period) / duration of treatment period [in days]

The treatment period (exclude optional ITI period) is defined as from the date and time of first study treatment, until the date and time of last infusion of study medication, or last visit, whichever is later.

- “24-hour rule”: No more than 1 bleeding episode in a calendar day is counted. If there is more than 1 bleeding episode in a calendar day, to determine which bleeding episodes are counted, priority is given to treated bleeding episodes, spontaneous or trauma bleeding episodes, then joint bleeding episodes. Otherwise, the first bleeding episode in the day is counted. Severity and treatment response will be the worst value of the bleeding episodes of the day. The bleeding site will be aggregated over all bleeding events from that day. Regardless of which bleed is selected, the time of the first bleed in the day will be used. All other infusions in the day for treating bleeds will be considered follow-up infusions.
- “72-hour rule”: A spontaneous joint or spontaneous muscle bleeding episode will not be counted if it occurs within 72 hours of a prior bleeding episode (or infusion for that bleeding episode) at the same site. For a bleeding episode to be affected by this rule, all sites listed for the bleeding episode must be the same sites specified in the previous bleeding episode. If the current and previous bleeds are both skin/mucosa bleeds, this rule does not apply. Infusions for such bleeding episodes will be considered to be follow-up infusions.

See example below how these bleeds will be counted.

- Subject 1 reported => in analysis data set

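### SAP 6.2.1 words the primary ABR of all bleeds as spontaneous plus trauma bleeds, a limit by cause that the protocol does not set; the likely effect is small but only downward

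*SAP*

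**What the plan says.** SAP 6.2.1 gives the primary endpoint of each part as the "ABR of all bleeding episodes (sum of spontaneous bleeds and trauma bleeds exclude bleeding due to surgery" and then closes the parenthesis; Part B adds the 48-hour window after a prophylaxis infusion.

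The protocol has no such parenthesis. Section 7.3: "The primary efficacy variable in Part A is the ABR of all bleeding episodes during prophylaxis". Section 9.4.2: "The primary endpoint in Part A is the ABR of all bleeding episodes during prophylaxis treatment". Both sections word Part B in the same way, with the 48-hour window added.

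The formula, the same in Protocol 9.4.1 and SAP 4.5, is "365.25 [days per year] x (# of bleeding episodes in treatment period) / duration of treatment period [in days", closing bracket omitted. Both documents attach a 24-hour and a 72-hour rule. SAP 4.5 adds: "Bleeds occurring before start of prophylaxis treatment with study medication will not be counted". None of these limits the endpoint by cause. The 72-hour rule names spontaneous joint and muscle bleeds, but only to merge repeat bleeds at one site.

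SAP section 7 logs the parenthesis as added detail in version 2.0 (17 November 2021). Protocol version 4.0 (12 May 2023) is later and does not contain it.

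**The concern.** The two documents give different numerators for the primary endpoint. If spontaneous and trauma together cover every bleed, the difference is only the surgery exclusion. If they do not, a recorded bleed with neither label meets the protocol definition and fails the SAP definition. Each such omission lowers the ABR; none can raise it.

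The study is descriptive, so the estimate itself is the result, and Protocol 9.4.1 plans a numerical comparison with the LEOPOLD trials. A literal reading would also be inconsistent within the SAP. A joint bleed with no recorded cause would count in the joint-bleed summary of SAP 6.2.2 but not among all bleeds. SAP 6.2.2 also uses the word total without saying whether the same limit applies.

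**Working it through.** **1. The plan's own precision figure.** Protocol 9.2.1 assumes mean 4, SD 5, n = 30. Half-width = 1.96 × 5/√30 = 1.79, interval 2.21 to 5.79. This matches the stated 1.8 and 2.2 to 5.8. It does not depend on the definition and serves here as a yardstick.

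**2. Can a bleed fall in neither class?** Yes, on the documents' own terms.
- The 24-hour rule ranks same-day bleeds: "priority is given to treated bleeding episodes, spontaneous or trauma bleeding episodes, then joint bleeding episodes". The second rank has work to do only if some bleeds are neither spontaneous nor trauma.
- Diary item b in Protocol 7.3.1 puts cause values and site values in one list with a catch-all category. No text requires a cause to be chosen.
- SAP 4.5 says: "If an infusion is given for a bleed and the bleed information is not provided, the infusion date will be used" as the bleed date. It supplies a date but no cause. SAP 4.3 ends: "Other missing data will not be imputed".
- For a home infusion, the reason code may supply the cause, since first treatment of a bleed is coded as spontaneous or trauma. An untreated bleed has no infusion code.

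**3. How often did it happen before?** Counts are from the package insert (Protocol section 12, Tables 6, 7 and 13). Neither class = total − (spontaneous + trauma).

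| Group | Total | Spontaneous + trauma | Neither | Share |
|---|---|---|---|---|
| Study 1, main | 241 | 153 + 79 = 232 | 9 | 3.7% |
| Study 1, extension | 154 | 79 + 70 = 149 | 5 | 3.2% |
| Study 2, prophylaxis | 293 | 209 + 74 = 283 | 10 | 3.4% |
| Study 3 (children), treated bleeds | 81 | 20 + 59 = 79 | 2 | 2.5% |
| Chinese prophylaxis subgroup | 67 | 46 + 16 = 62 | 5 | 7.5% |

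The Chinese subgroup is part of Study 2. Without it, Study 2 gives (10 − 5)/(293 − 67) = 5/226 = 2.2%. On demand, the shares are 3/1204 = 0.2% and 2/432 = 0.5%. Most of these bleeds are described as uncharacterized. Two were in neither class even after those were removed: 150 − 149 = 1 (Study 1 extension) and 1202 − 1201 = 1 (Study 2 on demand).

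**4. Effect if shares of 2.5% to 7.5% applied here (an assumption).**
- Part A children: 4 × 2/81 = 0.10 and 4 × 5/67 = 0.30 per year, about 5% to 17% of the half-width of 1.8. Expected bleeds are 30 × 0.5 year × 4 = 60, so 1.5 to 4.5 bleeds would be lost.
- Part B: 1.9 × 2/81 = 0.05 and 1.9 × 5/67 = 0.14 per year. Protocol 7.2.8 expects 6 to 12 months, so 6 × 0.5 × 1.9 = 5.7 to 6 × 1 × 1.9 = 11.4 bleeds, of which 0.14 to 0.85 would be lost.
- One omitted bleed over six months lowers that participant's ABR by about 2.0. The group mean moves by 2/30 = 0.07 in Part A children, or 2/6 = 0.33 in Part B.

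**5. Did the comparison ABRs count such bleeds?** Crude rates against the published means:

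| Source | All bleeds | Spontaneous + trauma | Published |
|---|---|---|---|
| Study 1 | 241/62 = 3.89 | 232/62 = 3.74 | 3.8 |
| Study 2 | 293/59 = 4.97 | 283/59 = 4.80 | 4.9 |
| Children | 97 × 365.25/(51 × 182) = 3.82 | 95 × 365.25/(51 × 182) = 3.74 | 3.75 |
| Chinese subgroup | 67/17 = 3.94 | 62/17 = 3.65 | 3.91 |

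Studies 1 and 2 assume about one year each. The children's row uses the median of 182 days and takes the 16 bleeds outside the 81 as having a cause. These three rows do not settle the question. For the Chinese subgroup, the insert says all 17 were treated for at least 12 months. Each rate is then at most its bleed count, so 62 bleeds give a mean of at most 3.65 (3.70 if 12 months means 360 days). That is below 3.91, which needs 66 or 67 of the 67 bleeds.

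**The case against.** The strongest reply is that an exhaustive split was meant. The change log calls the parenthesis a detail, the sentence still says all bleeding episodes, and the only exclusion it names is surgery. Dating a bleed from its infusion would be odd if that bleed were then discarded. This is a fair reading of intent, but the wording does not say so, and intent is not a counting rule.

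Second, SAP section 1 places dataset and data-handling details in separate specifications that it treats as part of the SAP. A rule for a missing cause could be there. This stands: one can say only that the available text has none.

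Third, the routes to an unlabelled bleed are narrow. The diary offers a cause for every bleed, home treatment codes carry one, and entries are verified. This also stands, so the loss may be nil. SAP 6.2.2 summarizes other bleed types separately, so such bleeds need not vanish from the report. Those types may be sites, however, and a separate summary would not restore the bleeds to the primary ABR.

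Fourth, 7.5% is a weak upper end: five bleeds among 17 participants, in a Chinese subset with only one adolescent, applied to children. This is correct. The paediatric 2.5% is nearer the target population, although Table 7 gives no cause for 16 of its 97 bleeds.

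**Conclusion.** The conflict stands as a matter of wording. The SAP states a narrower numerator than the protocol, and the documents show that the two classes need not cover every bleed. The likely size is small: about 0.1 per year on a mean of 4 at 2.5%, up to 0.3 at 7.5%, and under one bleed across Part B. These figures assume that package-insert shares carry over. The effect is zero if every bleed receives a cause. No test, sample size or planned half-width changes. Excluding surgical bleeding is compatible with the separate minor-surgery endpoint, but the protocol's primary endpoint does not state it.

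Two stronger inferences are not supported:
- A reader might infer that only two of the diary's seven bleed types count. The list mixes causes and sites, so a joint or muscle bleed can also be spontaneous or traumatic and then stays in.
- A reader might infer that the LEOPOLD comparators in general counted unlabelled bleeds, so that this trial would look better against all of them. Only the Chinese subgroup indicates this. It does so only if the 12-month statement holds and the reported bleed count is the ABR numerator. The children's mean of 3.75 is nominally closer to spontaneous plus trauma. For LEOPOLD Kids Part B, the Part B reference, the documents give no bleed counts.

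**What to change.** In SAP 6.2.1, define the total ABR as every bleeding episode remaining after the SAP 4.5 rules (start of prophylaxis, 24-hour, 72-hour), plus the 48-hour window for Part B, including bleeds of other or unrecorded cause. Give the word total in SAP 6.2.2 the same meaning. Show spontaneous, trauma and other/unclassified as components that add up to the total. If bleeding due to surgery is to be the one exclusion, state it identically in protocol and SAP and list the bleeds excluded. If the separate dataset specifications already classify bleeds without a cause, bring that rule into the SAP text.

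The cost is a few lines of SAP wording, one table row and, if the surgery exclusion stays, a matching protocol sentence. A sensitivity line restricted to spontaneous plus trauma is optional. The reported ABR may be slightly higher than under the literal SAP wording. If no bleed is unclassified, counting them changes no result.

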#### 6.2.2 Secondary Endpoint(s)

Spontaneous bleeding episodes, trauma bleeding episodes, joint bleeding episodes, and other bleeding episodes types will be summarized separately.

Other efficacy variables are:

- ABR of treated bleeding episodes (total, joint, spontaneous, trauma)
- ABR of target joint bleeding episodes
- ABR of bleeding episodes within 48h of previous prophylaxis infusion (total, joint, spontaneous, trauma) [for Part A]
- ABR of total bleeding episodes during prophylaxis treatment [for Part B]
- Study participant's/caregiver's assessment of response to treatment of bleeding episodes (excellent, moderate, good, or poor)
- Physician's assessment of the response to treatment of bleeding episodes in minor surgery (excellent, moderate, good, or poor)
- Evaluate proportion of patients without bleeding episodes
- The number of infusions per bleeding episode
- Factor VIII usage (expressed as number of infusions and IU/kg per year, as well as
- IU/kg per event)
- Incremental recovery

For subjects undergoing surgery (both major and minor), number of surgery infusions, and total doses will be summarized and listed for these subjects.

## Statistical Analysis Plan

BAY 81-8973 (KOVALTRY) / 19855

Page: 12 of 15

Factor VIII concentration values and recovery values will be summarized by time point.

$$\text{recovery} = (\text{post-infusion FVIII} - \text{pre-infusion FVIII}) * \text{weight / dose (in IU)}$$

If a Factor VIII concentration value is below the LLOQ (lower limit of quantification), a data point will be substituted by one half of this limit.

A validity flag for recovery values and their corresponding pre- and post-infusion FVIII values will be created. These values will be considered valid except when any of the following conditions apply:

- If pre-infusion FVIII  $\geq$  post-infusion FVIII [biologically impossible in the absence of inhibitors]
- If pre-infusion FVIII  $> 40$  IU/dl (note 1 IU/dl=1%) [protocol violation]
- If post-infusion FVIII  $< 10$  IU/dl (note 1 IU/dl=1%) [biologically impossible in the absence of inhibitors]

In the tables displaying descriptive statistics of recovery values, if a recovery is flagged as not valid, then the corresponding pre-infusion FVIII, post-infusion FVIII, and recovery values will not be included.

Furthermore, if there are multiple FVIII values for a subject and timepoint, only the record with the lowest LLOQ will be used. The others values will be excluded from the analysis dataset.

Besides the efficacy variables will be analyzed in summary statistics by age group (<12 or  $\geq$ 12 years of age), if it is applicable, the efficacy endpoints of ABR will also be estimated by a negative binomial regression with duration of treatment period as offset variable.

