### 7.3.2 Incremental Recovery of KOVALTRY

Incremental recovery will be determined by collecting a sample for KOVALTRY level before the scheduled infusion, and a second sample collected 15 to 30 min after end of the infusion.

Blood samples for KOVALTRY trough (predose) and recovery levels (15 to 30 min post infusion) will be collected in all participants at Visits 2, 4, and 5 in Part A; at Visits 2, 6, and 8 in Part B; and at additional time points based on the investigator's discretion. Infusions must be given in hospital and use the participants assigned treatment dose, rounded to full vial size.

The exact times for infusion and blood sampling before and after infusion and the dose administered will be documented in the CRF.

Infusions given at study visits will be recorded in the site participant records, which will be the source documents and will be used to enter this information in the CRF.

The samples will be collected as described in detail in the laboratory manual. All samples will be processed in the central laboratory (Part A) or local laboratory (Part B). Plasma concentrations of FVIII will be measured using a validated FVIII activity assay ("chromogenic assay" for Part A, "one-stage clotting assay" for Part B).

Samples for incremental recovery should be collected on days when the next prophylactic infusion is scheduled and at least 48 h after the last infusion prior to this. The measurements should only be performed when the participant is not actively bleeding and when FVIII:C levels are close to trough.

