#### 9.4.1 General Considerations

There is no confirmatory comparison planned for this study; study results will be numerically evaluated and compared with the data in the completed LEOPOLD Clinical Trials.

Efficacy analyses outlined in this section only include the data from Part A or Part B (i.e., data from the Optional ITI Treatment are excluded).

For the efficacy endpoints, bleeding events will be presented as summary statistics by age groups.

The annualized bleeding rates for each participant are estimated via

$$\text{Annualized bleeding rate [per year]} = \frac{365.25 \text{ [days per year]} \times (\text{\# of bleeding episodes in treatment period})}{\text{duration of treatment period [in days]}}$$

The treatment period is defined as from the date and time of first study treatment until the date and time of last infusion of study medication, or last visit, whichever is later (not including the Optional ITI Treatment). Before this period is the screening period, after this period is the follow-up period.

Further, for the derivation of analysis variables for bleeding episodes, the following rules will apply:

- “24-hour rule”:  
No more than 1 bleeding episode in a calendar day is counted. If there is more than 1 bleeding episode in a calendar day, to determine which bleeding episodes are counted, priority is given to treated bleeding episodes, spontaneous or trauma bleeding episodes, then joint bleeding episodes. Otherwise, the first bleeding episode in the day is counted. Severity and treatment response will be the worst value of the bleeding episodes of the day. The bleeding site will be aggregated over all bleeding events from that day.
- “72-hour rule”:  
A spontaneous joint or spontaneous muscle bleeding episode will not be counted if it occurs within 72 hours of a prior bleeding episode (or infusion for that bleeding episode) at the same site. For a bleeding episode to be affected by this rule, all sites listed for the bleeding episode must be the same sites specified in the previous bleeding episode. If the current and previous bleeds are both skin/mucosa bleeds, this rule does not apply. Infusions for such bleeding episodes will be considered to be follow-up infusions.

Missing information on date and time of bleeding episodes will be substituted by the date and time of first treatment, if available.

Further handling of missing data will be described in the SAP.

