**Table 10–1: Recommended Blood Draw Volume**

Body Wt. (kg)	Body Wt. (lbs)	Total blood volume (mL)	Allowable volume (mL) in one blood draw (1% of total blood volume)	Total volume (mL) drawn in a 30-day period (3% of total blood volume)
1	2.2	100	1	3
2	4.4	200	2	6
3	6.3	240	2.4	7.2
4	8.8	320	3.2	9.6
5	11	400	4	12
6	13.2	480	4.8	14.4
7	15.4	560	5	16.8
8	17.6	640	6.4	19.2
9	19.8	720	7.2	21.6
10	22	800	8	24

Abbreviations: Wt.: Body weight

Source: (15)

For infants of at least 7 kg at study enrollment, the volumes listed for each individual visit should be well tolerated.

The tests described in Section 8.3 and listed in Table 10–2 will be performed by the central laboratory (Part A, investigators will be provided with a laboratory manual for instructions on how to collect and process samples) or local laboratory (Part B). For part A if a local sample analysis is required, it is important that the sample for central analysis is obtained at the same time. Additionally, if the local laboratory results are used to make either a study intervention decision or response evaluation, the results must be entered into the CRF. For part B, a separated page for local laboratory results will be available in eCRF.

Protocol-specific requirements for inclusion or exclusion of participants are detailed in Section 5 of the protocol.

Additional tests may be performed at any time during the study as determined necessary by the investigator or required by local regulations.

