**Table 16: Pharmacokinetic Parameters [Arithmetic Mean  $\pm$  SD] for KOVALTRY (50 IU/kg dose), One-Stage Clotting Assay**

Parameter [unit]	12 to 17 yrs (N=5)	$\geq$ 18 yrs (N=21)
AUC [IU $\cdot$ h/dL]	1013.9 $\pm$ 286.8	1601.3 $\pm$ 520.0
C max [IU/dL]	91.7 $\pm$ 28.7	99.7 $\pm$ 14.9
t 1/2 [h]	11.7 $\pm$ 1.11	14.3 $\pm$ 3.7
MRT IV [h]	16.1 $\pm$ 0.8	19.8 $\pm$ 5.7
V ss [dL/kg]	0.85 $\pm$ 0.24	0.63 $\pm$ 0.11
CL [dL/h/kg]	0.053 $\pm$ 0.017	0.035 $\pm$ 0.012

AUC: area under the curve

Cmax: maximum drug concentration in plasma after single dose

t1/2: terminal half-life

MRTIV: mean residence time after an IV administration

Vss: apparent volume distribution at steady-state

CL: clearance

The PK parameters of KOVALTRY for 8 subjects in age group 0 to <6 years and 10 subjects in age group 6 to <12 years are shown in Table 17. In general, children <12 years of age demonstrated lower plasma concentrations when compared to PTP children  $\geq$ 12 years of age.

**Table 17: Pharmacokinetic Parameters [Arithmetic Mean  $\pm$  SD] for KOVALTRY (50 IU/kg dose), Chromogenic Substrate Assay**

Parameter [unit]	0 to <6 yrs (N=8)	6 to <12 yrs (N=10) b	12 to 17 yrs (N=5)	$\geq$ 18 yrs (N=21)
AUC [IU $\cdot$ h/dL]	1544.7 $\pm$ 387.1 a	1214.5 $\pm$ 395.1	1572.0 $\pm$ 448.0	2103.4 $\pm$ 702.8
C max [IU/dL]	89.6 $\pm$ 27.4	81.6 $\pm$ 17.8	132.5 $\pm$ 46.3	133.1 $\pm$ 20.4
t 1/2 [h]	12.1 $\pm$ 2.7 a	12.0 $\pm$ 2.1	14.4 $\pm$ 5.5	14.2 $\pm$ 3.5
MRT IV [h]	17.7 $\pm$ 3.6 a	17.8 $\pm$ 2.9	19.8 $\pm$ 5.8	19.9 $\pm$ 4.9
V ss [dL/kg]	0.57 $\pm$ 0.13 a	0.79 $\pm$ 0.23	0.71 $\pm$ 0.39	0.50 $\pm$ 0.11
CL [dL/h/kg]	0.033 $\pm$ 0.009 a	0.045 $\pm$ 0.016	0.034 $\pm$ 0.010	0.027 $\pm$ 0.010

an=7

bOne subject considered PK outlier was excluded

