### 1. Introduction

This statistical analysis plan (SAP) version 2.0 is based on the finalized Protocol Version 2.0, dated 22 OCT 2020.

The protocol version 2.0, dated 22 OCT 2020 is integration of the original protocol version 1.0, dated 29 Jan 2020 and the amendment 1.

This SAP describes the study objective, study design, analysis sets, all endpoints, and statistical analysis methods. Complete details of Tables, Listing and Figures (TLFs) specifications as well as dataset details and data handling specifications will be provided in separate “TLF specifications” and “Analysis Datasets” documents as an integral part of this SAP.

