### 4. General Statistical Considerations

#### 4.1 General Principles

There is no confirmatory comparison planned for this study, study results will be numerically evaluated.

Part A and Part B will be analyzed separately, both for efficacy and safety. The optional ITI treatment period will only be considered for the safety analysis.

The efficacy and safety analysis will be presented as summary statistics by age groups (<12 or  $\geq 12$  years of age) in Part A.

The statistical evaluation will be performed by using the software package SAS release 9.2 or higher (SAS Institute Inc., Cary, NC, USA). All variables will be analyzed by descriptive statistical methods. The number of data available and missing data, mean, standard deviation, minimum, quartiles, median, and maximum will be calculated for metric data. Frequency tables will be generated for categorical data.

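### The SAP picks among multiple FVIII values by lowest LLOQ regardless of assay or laboratory, and does not reflect the assays that Protocol 4.0 assigns to each part

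*SAP*

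**What the plan says.** - **SAP 6.2.2, recovery.** "Factor VIII concentration values and recovery values will be summarized by time point". Recovery is the post-infusion minus the pre-infusion value, times weight, divided by dose. If a participant has more than one FVIII value at a time point, "only the record with the lowest LLOQ will be used". Neither rule refers to assay or laboratory.
- **SAP 1.** The SAP "is based on the finalized Protocol Version 2.0, dated 22 OCT 2020". The current protocol is version 4.0 of 12 May 2023.
- **Protocol 7.3.2.** "Plasma concentrations of FVIII will be measured using a validated FVIII activity assay": chromogenic in the central laboratory for Part A, one-stage clotting in the local laboratory for Part B.
- **Protocol 10.2.** For Part A, "if a local sample analysis is required, it is important that the sample for central analysis is obtained at the same time". Local results used for a treatment decision or a response evaluation have to be entered in the CRF. Table 10–2 lists FVIII level among the tests covered.
- **SAP 4.1.** "Part A and Part B will be analyzed separately, both for efficacy and safety".
- **Protocol 9.4.1.** Study results will be evaluated numerically and "compared with the data in the completed LEOPOLD Clinical Trials".

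**The concern.** Selecting by LLOQ is reasonable when all records come from one assay in one laboratory. It is not a safe criterion once two assays and two kinds of laboratory are in play, because the more sensitive record need not be the one the protocol designates. The rule works record by record for a participant and time point, so nothing ties the choice of the pre-infusion value to the choice of the post-infusion value.

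Two artefacts are possible. In Part A, a local value could displace the assigned central chromogenic value, at one or both ends of a pre/post pair. In Part B, values from before and after the change of assay could sit in one summary. Either way, an assay difference could be read as a difference between participants, between time points, or between this study and earlier ones. In vivo recovery is a secondary endpoint in both parts.

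**Working it through.** The plan attaches no sample size, power or precision figure to recovery, so there is no design figure to reproduce. The check is whether the rule can do harm, and how large the assay gap is in the label attached to the protocol.

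**1. Can the rule select the wrong record?**

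In Part A four things would have to coincide:

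- a local FVIII level is taken at a recovery time point (foreseen in Protocol 10.2);
- it reaches the database (required in 10.2 when it drives a decision);
- its LLOQ is lower than the central one (the documents give no LLOQ);
- the local assay is not chromogenic. The documents do not name a local assay for Part A. The Amendment 2 rationale, written for Part B, says that local laboratories do not have the chromogenic assay.

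The three validity conditions in SAP 6.2.2 (pre-infusion not below post-infusion, pre-infusion above 40 IU/dL, post-infusion below 10 IU/dL) do not test for assay. They would not in general detect a mixed pair.

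**2. Size of the assay gap in recovery (label Table 18, age 12 and over)**

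Gap = 1 − one-stage / chromogenic, on medians in IU/dL per IU/kg.

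| Source | Chromogenic | One-stage | Gap |
|---|---|---|---|
| Study 1 (N=59) | 2.5 | 2.2 | 1 − 2.2/2.5 = 12.0% |
| Study 2 (N=56) | 2.1 | 2.1 | 0.0% |
| Pooled (N=115) | 2.3 | 2.2 | 1 − 2.2/2.3 = 4.3% |

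**3. Outer bound from Cmax (label Tables 16 and 17)**

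Table 16 gives values "for KOVALTRY (50 IU/kg dose), One-Stage Clotting Assay"; Table 17 gives the chromogenic counterpart at the same dose.

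- 18 years and over (N=21): 1 − 99.7/133.1 = 25.1%
- 12 to 17 years (N=5): 1 − 91.7/132.5 = 30.8%

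Cmax bears on recovery because recovery is the rise per IU/kg. At 50 IU/kg, with a pre-infusion level near zero (an assumption), the adult figures correspond to 133.1/50 = 2.66 and 99.7/50 = 1.99.

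**4. Effect on a group mean**

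Assume equal true recovery across participants, and apply the gap from patients aged 12 and over to younger children. Neither can be verified from the documents. With k of n values by one-stage and the rest chromogenic, the shift is gap × k/n.

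| Situation | 12% gap | 25% to 31% gap |
|---|---|---|
| Part A, 1 of 30 children | 0.4% | 0.8% to 1.0% |
| Part A, 1 of 12 adolescents/adults | 1.0% | 2.1% to 2.6% |
| Part B, 1 of 6 | 2.0% | 4.2% to 5.2% |
| Part B, 3 of 6 | 6.0% | 12.5% to 15.5% |

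At the pooled 4.3% gap, 3 of 6 gives 4.3% × 3/6 = 2.15%. At Study 2's gap every shift is zero. For the individual whose post-infusion value was exchanged, the error is about the full gap.

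**5. Comparison with the label's paediatric values**

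The label's recoveries for previously treated children (Table 19) are chromogenic, with a starting median of 1.6 at 0 to under 6 years. At the recovery gap, the same blood would read 1.6 × 2.2/2.5 = 1.4 up to 1.6 by one-stage. At the extreme Cmax ratio it would read 1.6 × 91.7/132.5 = 1.1. The label has no one-stage data under 12 years to narrow this.

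**The case against.** The case for leaving the SAP alone has several sound parts.

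- **Pooling across parts.** A reader might infer that the SAP pools chromogenic Part A values with one-stage Part B values. It does not. SAP 4.1 separates the parts, and under Protocol 7.3.2 that is also the assay split.
- **A 25% to 31% error in recovery.** A reader might take this from the label's Cmax tables. For recovery itself the label describes the two assays as giving similar values, with medians 0% to 12% apart. It also cites a 41-laboratory field study in which either assay measured activity accurately. The Cmax tables rest on 26 patients, five of them aged 12 to 17.
- **A false change from baseline.** The SAP plans no such statistic for recovery, only summaries by time point. Change from baseline is specified for laboratory values and vital signs.
- **Mixed assays in Part B as a fact.** The documents do not show that any Part B sample was analysed before Amendment 2. Under the current protocol, local laboratories without the chromogenic assay would not generate cross-assay duplicates.
- **LEOPOLD comparison.** The chromogenic paediatric recoveries come from previously treated children, whose counterpart is Part A, also chromogenic. Protocol 9.4.1 does not single out recovery for comparison.
- **Unseen documents.** SAP 1 places data-handling detail in separate specifications that may settle some of this.

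All of this limits the size and certainty of the point. It does not remove it: the lowest-LLOQ rule is a stated rule, it ignores assay and laboratory, and the protocol foresees the parallel samples on which it could act.

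**Conclusion.** The point holds in a limited form. The SAP's rule for multiple FVIII values can override the assay and laboratory that Protocol 7.3.2 assigns in Part A, and can pair pre- and post-infusion values from different assays. It also has no provision for a Part B summary containing both assays, should that have occurred.

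The likely size is small: 0% to 12% for an affected recovery value, 4.3% on the label's pooled medians, and much less on a Part A group mean unless duplicates are common. In Part B, with about six children, a half-and-half mix would shift the mean by 0% to 6.0%. The Cmax-based 12.5% to 15.5% is an outer bound only.

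These figures rest on label data from patients aged 12 and over; the gap in younger children is not documented. Whether duplicates or pre-amendment Part B samples exist is unknown. The endpoint is secondary and descriptive, and no test or sample size depends on it. The change is still worth making, because it costs little and the SAP needs aligning with Protocol 4.0 in any case.

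**What to change.** 1. Update the SAP to Protocol 4.0 and state the assay and laboratory for FVIII levels and recovery in each part.
2. For multiple values, select by protocol-assigned assay and laboratory first, and by LLOQ only among records that tie on both.
3. Calculate recovery only from pre- and post-infusion values measured by the same assay.
4. If Part B contains both assays, tabulate its FVIII levels and recovery by assay.
5. State the assay in any numerical comparison of Part B recovery with Part A or with the label's chromogenic paediatric values.

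Step 4 needs assay and LLOQ on each record, so confirm that the planned Part B local-laboratory eCRF page captures them.

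The cost is an SAP amendment and, if the fields are missing, two eCRF fields. No extra sample or visit is needed.
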